2. INTRODUCTION

Augmentin is an oral antibacterial combination of the semisynthetic beta-lactam antibiotic, amoxicillin, and the beta-lactamase inhibitor clavulanate potassium. The presence of clavulanate potassium in Augmentin protects amoxicillin from degradation by beta-lactamase enzymes and effectively extends the antimicrobial spectrum of amoxicillin to include many gram-negative aerobic and anaerobic bacteria. It is indicated for use when amoxicillin-resistant pathogens, such as those expressing beta lactamases, are suspected as a cause of respiratory tract and other infections.

Augmentin (ES)-600 is a high-dose amoxicillin/clavulanic acid (AMC/CVA) (14:1) formulation that allows administration at 90/6.4 mg/kg/day in two divided doses, double the previously recommended standard amoxicillin dosage without doubling the unit dose of potassium clavulanate in a fixed dose combination formulation, inhibitory activity of CVA against bacterial beta-lactamases is maintained. [\[AUGMENTIN ES-600 Prescribing Information, 2019\]](#)

Optimizing the PK/PD (ie, T>MIC values) of Augmentin (ES)-600 (14:1) maximizes bacterial eradication such as *Streptococcus pneumoniae* (including penicillin-resistant *S. pneumoniae* (PRSP); MIC 2-4 ug/mL), *Haemophilus influenzae* (*H. influenzae*) and *Moraxella catarrhalis* (*M. catarrhalis*); principal respiratory pathogens implicated in Acute Respiratory Tract Infections (ARTIs) in children. This assures highest probability of clinical cure, thus reducing the spread and development of resistance. Augmentin (ES)-600 therefore plays an important role in the management of ARTIs in children.

2.1. Study Rationale

Due to non-availability of Augmentin (ES)-600 in India, most physicians can only use available standard Augmentin 7:1 (45/6.4 mg/kg/day) formulation and double the dose to achieve the guideline recommended higher dose of amoxicillin at 90 mg/kg/day in ARTIs in children. However, using the 7:1 formulation causes unnecessary exposure to higher proportionate dose of CVA (12.8 mg/kg/day) as a unit dose of 6.4 mg/kg/day of CVA is only required for efficacy against beta-lactamase producing respiratory pathogens. Hence, there is an unmet need for availability of Augmentin (ES)-600 in India.

The safety profile of AMC/CVA is also well understood. Most adverse events are mild and transient. Main adverse effects (in adults and children) include gastrointestinal (GI) disturbances, including diarrhoea, nausea, vomiting and indigestion (each <5% incidence). [\[Todd PA et al, 1990\]](#) [\[Huttnner A et al, 2020\]](#) [\[Easton J et al, 2003\]](#) [\[Bottenfield GW et al, 1998\]](#) [\[Dietz H et al, 1999\]](#)

In this regard, the Indian Regulatory Agency (CDSCO) has granted a marketing authorization on 08 June 2020 for import/marketing of Augmentin (ES)-600 in India to the Sponsor (GlaxoSmithKline), with a post marketing commitment to conduct a

Phase IV study in India, whose purpose is to generate safety data on Augmentin (ES)-600 in paediatric population in India.

To this effect, the current study is designed to assess the safety and clinical efficacy of Augmentin (ES)-600, AMC/CVA (14:1) at 90/6.4 mg/kg/day in two divided doses every 12 hours in children (age between 6 months and 12 years) with ARTIs, including Acute otitis media (AOM), Acute bacterial rhinosinusitis (ABRS) and Community acquired bacterial pneumonia (CABP).

The purpose of this study is to confirm the safety and efficacy profile of Augmentin (ES)-600 in paediatric population in India.

2.2. Background

Acute respiratory tract infections (ARTIs) like acute otitis media, sinusitis and community-acquired pneumonia are a leading cause of infectious disease-related morbidity, hospitalization, and mortality among children worldwide, particularly in low-income countries.[[Williams BG et al, 2002](#)] [[World Health Organization. World health statistics, 2017b](#)] [[World Health Organization. Acute respiratory infections in children, 2017a](#)] Although, in children under 5 years, primary infections with viral pathogens can also predispose to secondary bacterial infections.[[Fan J et al, 1998](#)] [[Bellau-Pujol S et al, 2005](#)]

The most frequently isolated bacteria in ARTIs include *Streptococcus pneumoniae*, non-typeable *Haemophilus influenzae* and *Moraxella catarrhalis*.[[Marom T et al, 2014](#)] These bacteria were increasingly resistant to commonly used antibiotics for ARTI treatment, leading to increase in mortality rates, hospital durations, and health care-associated costs.[[Mauldin PD et al, 2010](#)] For instance, the increase in *S. pneumoniae* of intermediate susceptibility to penicillin-(PISP; penicillin MICs 0.12 to 1.0 μ g/mL), and many, but not all, highly resistant serotypes of PRSP (penicillin MICs, ≥ 2 μ g/mL) strains pose serious clinical problems.[[Camara M et al, 2017](#)] [[Yamanaka N et al, 2008](#)] [[Kim SH et al, 2012](#)]

Based on such trends, an increase in the daily dose of amoxicillin from 45 mg/kg to 90 mg/kg was introduced in late 2000 to respond to increasing presence of PRSP. This is because, amoxicillin, with or without clavulanate potassium, has one of the lowest MICs for *S. pneumoniae* among the available oral beta-lactam agents.[[Jacobs MR et al, 1999](#)] [[Geng Q et al, 2014](#)] [[Pan F et al, 2015](#)] [[Li QH et al, 2013](#)] [[Fu J et al, 2019](#)] Currently, most treatment guidelines on ARTIs recommend the use of higher doses of amoxicillin with or without clavulanic acid in ARTIs, mostly where PISP/PRSP is suspected.[[Dagan R et al, 2001](#)] [[Piglansky L et al, 2003](#)] [[Arrieta A et al, 2003](#)] [[Casellas JM Jr et al, 2005](#)] [[Block SL et al, 2006](#)] [[Chu CH et al, 2014](#)] [[Casey JR et al, 2012](#)] [[Hoberman A et al, 2017](#)] [[Lieberthal AS et al, 2013](#)]

For instance, in 2013 (reaffirmed in 2019), American Academy of Pediatrics recommended high-dose amoxicillin (80 to 90 mg/kg/day in 2 divided doses) for 5 to 10 days as preferred therapy in AOM.[[Lieberthal AS et al, 2013](#)] An alternative recommended first-line treatment is AMC/CVA at 90/6.4 mg per kg/day in 2 divided doses who have received AMC in the previous 30 days or having recurrent/persistent otitis media or who have the otitis-conjunctivitis syndrome.[[Lieberthal AS et al, 2013](#)]

In 2012 IDSA recommended “high-dose” AMC/CVA (90 mg/kg/day orally twice daily) for children with ABRS from geographic regions with high endemic rates ($\geq 10\%$) of invasive PRSP, those with severe infection (eg, evidence of systemic toxicity with fever of 39°C [102°F] or higher, and threat of suppurative complications), attendance at day-care, age < 2 years, recent hospitalization, antibiotic use within the past month, or who are immunocompromised.[[Anthony W et al, 2012](#)]

High dose amoxicillin (90 mg/kg/day) with or without clavulanic acid has also been recommended in CABP in children age > 3 months by American Academy of Pediatrics, British Thoracic Society, especially where higher rates of PRSP exist. Amoxicillin clavulanic acid is the preferred agent when empirical coverage of *H influenzae* and *M catarrhalis* is warranted (30% of *H influenzae* and 100% of *M catarrhalis* produce beta-lactamase).[[Messinger AI et al, 2017](#)] [[Ostapchuk M et al, 2004](#)]

Overall, the selection of high-dose AMC/CVA (90 mg/kg/day) in ARTIs has been made based on long-term safety of the drug; its efficacy against the key respiratory pathogens and a first choice-to-treat PRSP and beta-lactamase producing strains that have potential to cause disease recurrence or therapy failure.

Safety profile of AMC/CVA is also well understood. The most frequently reported adverse events are GI disturbances, including diarrhoea, nausea, vomiting and indigestion that can be reduced by taking AMC/CVA with food.[[Stein GE et al, 1984](#)] [[Easton J et al, 2003](#)] High-dose AMC/CVA (90/6.4 mg/kg/day) has shown similar tolerability profile to a conventional twice-daily regimen (45/6.4 mg/kg/day).[[Bottenfield GW et al, 1998](#)] Adverse events (AEs) were reported in a total of 50.2% and 47.3% of patients, with protocol-defined diarrhoea in 11% and 8.8% patients. The most frequently reported adverse events in 521 children treated with the high-dose formulation in another study were diaper rash (4.0%), diarrhoea (3.6%), vomiting (2.3%) and other rash (1.3%). Events probably or possibly related to the medication were documented in 14% of patients.

In summary, Augmentin ES-600 (AMC/CVA 14:1) has been developed based on a combination of PK/PD considerations, in vitro, in vivo animal, and clinical data, and primarily intended to treat ARTIs in cases where PRSP is suspected and beta-lactamase producing organism cannot be ruled out. Its safety profile is well understood and is comparable to conventional Augmentin dosing regimens.

2.3. Benefit/Risk Assessment

2.3.1. Risk Assessment

The risk/benefit considerations for therapy in ARTIs must also be extended to consider the environmental consequences of using sub-optimally effective antibiotics which may be drivers of the development and spread of antibiotic resistance. There has been clearly a need for alternative dosage regimens and to use measures to control and reduce the emergence of resistant organisms, particularly PRSP.

In this regard, time above MIC (T>MIC) data suggest that doses of AMC at 90 mg/kg/day administered in divided doses every 12 hours may provide concentrations of antibiotic sufficient to kill PRSP with MICs 2-4 $\mu\text{g}/\text{mL}$. This regimen was calculated to provide a T>MIC of 38% for an MIC of 4 $\mu\text{g}/\text{mL}$, in contrast to 23% of T>MIC provided by the current dose of 45/6.4 mg/kg/day given in divided doses every 12 hours. The low toxicity of amoxicillin and experience already gained with higher doses worldwide suggest that the increase in the daily dose of amoxicillin will be unlikely to adversely affect tolerability. In addition, presence of clavulanic acid in Augmentin (ES)-600 would provide coverage against beta-lactamase producing pathogens like as *H. influenzae* and *M. catarrhalis*, that are inherently resistant to amoxicillin. The rationale for dosage and administration is described in Section 4.3.

Overall, the broad spectrum of activity against aerobic and anaerobic Gram-positive and Gram-negative bacteria, together with a good PK/PD profile and well understood safety profile, makes Augmentin (ES)-600 a useful antimicrobial in limiting ARTIs and development of resistance.

The following section outlines the potential risk assessment and mitigation strategy for this protocol ([Table 1](#)).

Table 1 Potential Risk and Mitigation Strategy

Potential Risk of Clinical Significance	Summary of Data/Rationale for Risk	Mitigation Strategy
Investigational Medicinal Product (IP)		
Hypersensitivity reactions to study treatment and/or beta-lactams	
Global data sheet (GDS), , Prescribing Information/potential risk of fatal hypersensitivity (anaphylactoid) reactions have been reported in patients on penicillin therapy. These reactions are more likely to occur in individuals with a history of penicillin hypersensitivity.
	
Exclusion of subjects with a known hypersensitivity to any component of amoxicillin or clavulanic or beta-lactams, e.g. penicillins and cephalosporins acid and its excipients or history of a serious adverse reaction possibly related to any of these agents. (See exclusion criteria in Section 5.2).
 
In case of anaphylaxis or unanticipated hypersensitivity reaction, participant will be withdrawn and managed as per Investigator's discretion. However, such participants will have to return for safety assessment at scheduled FU visit.

Infectious mononucleosis	
GDS, Prescribing Information/ a morbilliform rash has been associated with this condition following the use of amoxicillin.
	
Exclusion of patients with an infectious mononucleosis. (See exclusion criteria in Section 5.2).

Pseudomembranous colitis and antibiotic associated diarrhoea	
GDS/ pseudomembranous colitis has been reported with the use of antibiotics and may range in severity from mild to life-threatening. It is important to consider its diagnosis in patients who develop diarrhoea during or after antibiotic use.
	
If prolonged or significant diarrhoea occurs or the participant experiences abdominal cramps, treatment should be discontinued immediately, and the participant should be investigated further as per Investigator's discretion.

Potential Risk of Clinical Significance	Summary of Data/Rationale for Risk	Mitigation Strategy
Hepatic Dysfunction	
GDS/ - amoxicillin-clavulanate-associated jaundice/hepatic dysfunction has been rarely reported.
 
GDS/A moderate rise in ALT and AST has been associated with use of - amoxicillin-clavulanate.
	Exclusion of patients with current hepatic impairment, or history of jaundice or hepatic impairment due to any component of Amoxicillin/Clavulanic acid. (See exclusion criteria in Section 5.2).
Renal Impairment	GDS/dose needs to be adjusted in patients with creatinine clearance less than 30 mL/min.	Exclusion of patients with known renal insufficiency e.g. plasma creatinine > 1.5 times upper limit of normal range for age. (See exclusion criteria in Section 5.2).
Phenylketonuria	GDS/ amoxicillin-clavulanate suspensions contain aspartame, which is a source of phenylalanine and so should be used with caution in patients with phenylketonuria.	Exclusion of patients with phenylketonuria.
Drug-Drug Interaction Potential	
GDS/ In common with other antibiotics, amoxicillin-clavulanate may affect the gut flora, leading to lower oestrogen re-absorption and reduced efficacy of combined oral contraceptives.
 
GDS/ Concomitant use of probenecid is not recommended. Probenecid decreases the renal tubular secretion of amoxicillin. Concomitant use with amoxicillin-clavulanate may result in
	
This subject population is unlikely to be on OCP.
 
The use of Probenecid is to be prohibited during the study. Patients should be excluded who are on Probenecid.

Potential Risk of Clinical Significance	Summary of Data/Rationale for Risk	Mitigation Strategy
	
increased and prolonged blood levels of amoxicillin, but not of clavulanic acid.
 
GDS/ In the literature there are rare cases of increased international normalised ratio in patients maintained on acenocoumarol or warfarin and prescribed a course of amoxicillin. If co-administration is necessary, the prothrombin time or international normalised ratio should be carefully monitored with the addition or withdrawal of amoxicillin.
	
This population is unlikely to be on warfarin. If participants are on Warfarin, they should be excluded from study.

Pregnancy/Lactation	
GDS/Reproduction studies in animals (mice and rats at doses up to 10 times the human dose) with orally and parenterally administered amoxicillin-clavulanate have shown no teratogenic effects. In a single study in women with pre-term, premature rupture of the fetal membrane (pPROM), it was reported that prophylactic treatment with amoxicillin-clavulanate may be associated with an increased risk of necrotizing enterocolitis in neonates.
	
Augmentin is not contraindicated in pregnancy. Details of all pregnancies in female participants will be collected at Day 0.
 
Participants will be instructed to notify the Investigator if they become pregnant during study period. Such participants will be immediately withdrawn from the study.
 
Any reported pregnancy must be informed to Sponsor by Investigator within 24 hours of receipt of information and should follow the procedures outlined in Appendix 4.

Potential Risk of Clinical Significance	Summary of Data/Rationale for Risk	Mitigation Strategy
		Any abnormal pregnancy outcomes (eg, spontaneous abortion, fetal death, stillbirth, congenital anomalies, ectopic pregnancy) are considered SAE.
Exposure to ionizing radiation from X ray	
 - Since children demonstrate signs and symptoms of CAP differently than adults and may deteriorate more rapidly than adults, keeping an option of chest X ray in inclusion criteria is critical for investigators to rule out need for hospitalization. - Even if an X ray is only one radiological assay is required. (Only basis for the reference in addition of clinical judgement if needed) - There will be no follow up assay needed. The dose from a single chest X ray should not exceed 20 microsieverts and this corresponds to a lifetime risk of a fatal malignancy of about 1 in 1 million (ICRP 103), which falls into the 'trivial' risk category as defined by ICRP 62. malignancy of approximately 1 in 300,000). 	
 - The study will minimize exposure by using X rays acquired as part of clinical care whenever possible. - Robust study design and CRF will factor in detailed history, lab screening and clinical examination parameters which should reduce the need of radiation exposure in the pediatric age group patients. (It will be considered only if clinicians would like to have additional confirmation in addition of clinical decision) - All procedures will be performed by a qualified technician.

More detailed information about the known and expected benefits and risks and reasonably expected AEs of Augmentin (ES)-600 (14:1) may be found in the Prescribing Information.[[AUGMENTIN ES-600 Prescribing Information](#), 2019]

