5.2. Exclusion Criteria

Participants will be excluded from the study if they meet any of the following exclusion criteria:

1. Weight \geq 40 kg
2. Pre-existing renal insufficiency (eg, plasma creatinine >1.5 times upper limit of normal range for age)
3. Pre-existing liver disease(s) and/or hepatic dysfunction
4. A serious underlying disease as per clinician's judgment.
5. Currently having diarrhea at the time of screening
6. Concomitant infection which would preclude evaluation of the response to study intervention.
7. Concomitant condition precluding evaluation of clinical response (such as acute mastoiditis, facial palsy, bacterial meningitis, and brain tumor) that would preclude evaluation of the response to study intervention.
8. Congenital disorders such as maxillofacial dysplasia.
9. Spontaneous perforation of the tympanic membrane and drainage for longer than 24 hours.
10. Tympanoplasty tube(s) in place, or has anatomic abnormalities associated with recurrent AOM, prolonged middle ear effusion, including cleft palate or repair, high-arched palate, or Down's syndrome.
11. Severe cases of CABP including Hypoxemic, Septic, Ventilator-associated or hospital-acquired pneumonia
12. Need corticosteroid for systemic (inhalational steroids as controller therapy in asthma is allowed)
13. Infectious mononucleosis
14. Evidence of leukopenia and/or thrombocytopenia.
15. History of previous hypersensitivity reaction to penicillins, cephalosporins or other Beta-lactam antibiotics.
16. History of AMC/CVA-associated cholestatic jaundice/hepatic dysfunction.
17. History of phenylketonuria or a known hypersensitivity to aspartame.

18. Received, within 48 hours of study entry, or is scheduled to receive during the study period, any medication which may alter bowel function.
19. Currently receiving or has received more than one dose of systemic antibiotic therapy within one week prior to the initiation of the study.
20. Receipt of an investigational compound (non-FDA and non-DCGI approved) or device within the previous 30 days or five half-lives, whichever is longer, preceding the first dose of study intervention or during the study.
21. Participants with symptoms suggestive of active COVID-19 infection (ie, fever, cough, etc).
22. Participants with known COVID-19 positive contacts within the past 14 days.

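### Table 1 of the protocol says children on warfarin or probenecid should be excluded, but neither drug is among the 22 exclusion criteria in Section 5.2

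*Protocol*

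**What the plan says.** Protocol Section 2.3.1 introduces Table 1 with the sentence "The following section outlines the potential risk assessment and mitigation strategy for this protocol". The table is thus part of the protocol's instructions and not just background.

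Its drug-interaction row deals with warfarin and probenecid as follows.

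- **Warfarin.** The rationale column reports "rare cases of increased international normalised ratio in patients maintained on acenocoumarol or warfarin and prescribed a course of amoxicillin", and advises checking prothrombin time or INR if the drugs have to be given together. The mitigation column chooses exclusion instead of monitoring: "This population is unlikely to be on warfarin", and then "If participants are on Warfarin, they should be excluded from study".
- **Probenecid.** The mitigation column asks for two things: no use during the study, and exclusion of patients already taking it.

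Section 5.2 opens with "Participants will be excluded from the study if they meet any of the following exclusion criteria" and lists 22 numbered criteria. Under Section 5.4.2 the site assesses eligibility against the inclusion and exclusion criteria at the Preliminary Visit and records prior and concomitant medication at the same visit.

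Section 6.5 lets the investigator allow medication the child needs, rules out further antimicrobials, says that drugs affecting bowel habit are to be avoided, and prohibits probenecid-type drugs. It does not mention warfarin, and neither does the SAP.

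**The concern.** Two parts of one protocol give different answers to the same eligibility question. A reader of Table 1 would exclude a child on warfarin or probenecid; a reader of Section 5.2 would find no criterion that does so. Sites usually screen from the numbered list, and Section 8 requires them to confirm all eligibility criteria and allows no waivers. The drug would be seen when medication is recorded, but no numbered criterion tells the site to act on it.

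What is at stake is the safety of an individual child and the protocol's consistency with itself. Section 2.3.3 rests its benefit-risk conclusion partly on the measures taken to reduce risk, so a measure promised in Table 1 ought to be put into effect where eligibility is decided. The statistical analysis is not at stake.

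**Working it through.** No calculation applies beyond a count. The check sets Table 1 against Sections 5.2 and 6.5 and the scheduled tests.

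**Step 1. Exclusions stated in the Table 1 mitigation column.**

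| Exclusion in Table 1 | Criterion in 5.2 | Rule in 6.5 |
|---|---|---|
| Hypersensitivity | No. 15 (partial match) | – |
| Infectious mononucleosis ("Exclusion of patients with an infectious mononucleosis") | No. 13 | – |
| Hepatic impairment | Nos. 3 and 16 | – |
| Renal insufficiency | No. 2 | – |
| Phenylketonuria | No. 17 | – |
| Probenecid | None | Prohibited on study |
| Warfarin | None | Not mentioned |

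Stated exclusions: 7. With a full or partial counterpart in 5.2: 5. Without one: 7 − 5 = 2, namely probenecid and warfarin. Both come from the same row.

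The hypersensitivity match is partial. Table 1 also covers excipients and earlier serious reactions to these agents, whereas criterion 15 is limited to beta-lactam antibiotics and criterion 17 adds only aspartame.

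**Step 2. Could another criterion in 5.2 catch these drugs?** Four of the 22 criteria concern medication: no. 12 (systemic corticosteroid), no. 18 ("any medication which may alter bowel function"), no. 19 (recent systemic antibiotics) and no. 20 (investigational compounds). None covers an anticoagulant or probenecid. Criterion 4, serious underlying disease, could catch some anticoagulated children, but it depends on clinical judgement and does not refer to medication.

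**Step 3. Does Section 6.5 fill the gap?** For probenecid it does in part: use is barred on study, so a child taking it could not properly continue it. For warfarin it does not: the general permission for necessary medication would, on its wording, cover an anticoagulant.

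**Step 4. Would a scheduled test detect the interaction?** Table 10 in Appendix 2 lists haematology, creatinine, AST, ALT and bilirubin. It includes neither prothrombin time nor INR. The Schedule of Activities places laboratory evaluations at the Preliminary Visit only. Appendix 2 lets the investigator order further tests, but none is planned for this purpose.

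**Result.** Both drug exclusions are absent from 5.2. Probenecid has a second safeguard in 6.5; warfarin has none outside Table 1 apart from clinical judgement.

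**The case against.** The strongest reply is that the exclusion is already in the protocol. Table 1 is protocol text, so an investigator who has read it knows what to do. Medication is recorded at screening, criterion 4 gives discretion, and Section 6.5 leaves concomitant medication to the investigator's assessment. The interaction is described as rare and the drug as unlikely in this population. On this view, all that is missing is a copy of an instruction that already exists. This stands as to size. It does not remove the conflict, because the list that governs eligibility still omits two exclusions stated elsewhere.

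A reader might also infer more than the documents support:

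- **That Section 6.5 contradicts Table 1 on warfarin.** It does not. Table 1 asks for an on-study prohibition only for probenecid, and 6.5 contains it. For warfarin, Table 1 asks only for exclusion at entry.
- **That warfarin is the only exclusion not carried over.** That count holds only if an on-study prohibition is credited as an entry criterion for probenecid. Measured against 5.2 alone, two are missing.
- **That the missing cross-reference shows why the criterion was lost.** Four rows of Table 1 cite 5.2 and the drug-interaction row does not. But the phenylketonuria row also lacks the citation, and its criterion is in the list.
- **That acenocoumarol was meant to be excluded too.** It is named only in the rationale column; the mitigation column names warfarin alone.

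**Conclusion.** The point holds as a minor safety-consistency correction. Two of the seven exclusions in Table 1, warfarin and probenecid, have no criterion in Section 5.2. Warfarin is the weaker case, since it is mentioned only in Table 1 and no scheduled test would reveal the interaction.

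The likely number of children affected is few or none. This rests on Table 1's own statement about warfarin use; the documents give no frequency for either drug. The conclusion also assumes that sites screen mainly from the numbered list. The eCRF and the Study Reference Manual are not among the documents, so a safeguard placed there cannot be confirmed or ruled out. No estimate, sample size or study conclusion depends on this.

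**What to change.** **Needed**

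- Add to Section 5.2: *current use of warfarin or probenecid*.
- Cite Section 5.2 in the drug-interaction row of Table 1, as four other rows already do.

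**Optional**

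- Name acenocoumarol beside warfarin, since the same row attributes the interaction to both drugs. This would be a new exclusion and not the repair of an inconsistency.
- Add warfarin to the prohibited drugs in Section 6.5, so that starting it on study is covered as well.

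Once the entry exclusion is in 5.2, no INR test need be added at screening. The cost is one criterion and one cross-reference in the next amendment, plus a matching eligibility item in the eCRF if it has none. Medication is already recorded at the Preliminary Visit, so no new data are required, and the loss of recruitment should be negligible.
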